9.8.1.2 Follow up 1 (Day 10 +/- 2 days)

At the first follow up the device, either Zip 4 device or SoC sutures will removed at day 10(+-2 days). Prior discharge at visit 1 the subjects will receive instructions that if:

- 1) Treated with Zip 4 device the subject and their legal representative(s) will remove the subject themselves at day 10. If necessary, the subject/legal representative(s) may call the A&E for assistance during the removal.
- 2) Treated with SoC sutures the subject and their legal representative(s) will visit the Pediatric Emergency Department or at home for removal of the sutures. During the follow up after device removal the subject will be asked about any adverse events that may have occurred, and a review of the concomitant medication. The subject will be interviewed about the usage of the device, and will fill out the questionnaire, VAS, and photograph the laceration. Next follow up day 30 will be scheduled if not done at visit 1.

All of the above can be done in assistance by the legal representative(s), if needed.

The following assessments/procedures will be performed at follow up 1:

- Subject interview
- VAS
- Cosmetic Outcome
 - High definition photos will be taken of the laceration
 - Registration of any Adverse Events
- Registration of Concomitant Medication

9.8.1.3 Follow up 2 (Day 30 +/- 2 days)

At the second follow up the subjects will be asked about any adverse events that may have occurred and a review of concomitant medication. The subjects will fill out the questionnaire, Wound healing satisfaction, and a subject interview will be performed by the site personnel. Photographs will be taken on the laceration.

All of the above can be done in assistance by the legal representative(s), if needed.

If no pending adverse events the subjects will be assessed as completed and the subject termination page will be filled out in the CRF by the site personnel after the telephone call has been performed.

The following assessments/procedures will be performed at follow up 2:

- Subject interview
- Wound healing satisfaction questionnaire
- Cosmetic Outcome
 - High definition photos will be taken of the laceration
- Registration of any Adverse Events
- Registration of Concomitant Medication

9.8.2 Demographic Data and Baseline Measurements

The demographic data that is collected at the screening/baseline visit will describe the subject population and confirm eligibility. The age, gender and weight will be recorded. In addition,

relevant medical and surgical history, medicine review and physical examination of the laceration prior treatment.

Relevant medical and surgical history is defined as any previous or existing condition that may potentially affect the outcome of the treatment according to the best judgement of the investigator.

9.8.3 Performance Variables and Measurements

9.8.3.1 Time of treatment procedure

The treatment procedure time will be measured at the baseline/screening visit. The time will be recorded starting from the preparation of the wound until the protective wound dressing is applied. The time will be measured in HH:MM:SS, e.g. 01:15:30, and recorded in each subject's CRF.

9.8.3.2 Wound Evaluation Score (WES) -

The Wound Evaluation Score (WES) will be used to evaluate the scar satisfaction and appearance based on the photographs taken at day 0, day 10 and day 30. An independent panel of 2 Plastic Surgeons will objectively rate the photographs based on six categories. For each category, response is binary: either yes=0 or no/no=1.

9.8.3.3 Wound healing satisfaction

The wound healing satisfaction questionnaire will be filled out by the subject with assistance by the legal representative(s) if needed. The questionnaire will be used to achieve a subjective evaluation of the wound healing. The questionnaire will be filled out at day 30, and contain questions where the subject either will mark the most correct answer or rate on a line between 0-100 mm.

9.8.3.4 Visual Analog Scale (VAS)

The pain VAS is an instrument to measure pain intensity (15) to access the subject's subjective experience. The scale in this investigation will be between 0-100 mm, where 0 is no pain and 100 mm is the worst imaginable pain for the subject. The subject will fill out the VAS line at the point that represents their pain intensity at the time. The VAS will be used after device has been applied at day 0, and after device removal at day 10. Legal representative(s) will assist if needed.

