The Zip device has been commercially available since April 2013, with over 100.000 clinical cases in 30 countries in orthopedics, electrophysiology, dermatology, plastic and reconstructive surgery, vascular surgery, obstetrics and gynecology, and emergency medicine. Thus, the Zip device is not restricted to any particular procedure, and not either to a patient population. Randomized clinical investigations using the Zip device for skin closure in pediatric patients [6] as well as elderly patients [8] have demonstrated good clinical outcome.

Not only has previous studies showed to reduce the time in wound closure, but also that the Zip device is less painful during removal which might be especially beneficial for a pediatric population [6]. The CE-mark of the Zip device was affixed in 2014 and the device is commercially available in Sweden today.

This clinical investigation is designed to evaluate the time and costs savings and the satisfaction and outcomes of the Zip device when used in a Pediatric emergency department setting for repair of lacerations in a pediatric population. Previous studies have mainly showed the benefits when using the Zip device on surgical incisions, both in adults and pediatric patients, but not in a pediatric population requiring laceration repair. The investigation subjects will be

randomized to receive either the Zip device or standard of care wound closure using sutures for 10 days. All subjects will be followed up for 30 days after treatment.

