4.2 Clinical data

Previous clinical data, both from randomized investigations, case studies and evaluations, have shown the value of the Zip device in terms of ease of use in a timely manner, good cosmetic outcome and high patient satisfaction.

In 2013, a prospective case study was performed on subjects with skin excisions [9]. The results revealed that the Zip device was easy to use in a time efficient way with no requirements of advanced training to use the device effectively. The cosmetic outcome was good and high patient satisfaction with low ratings of pain during removal. No device-related complications were reported indicating the high safety of using the device.

In 2014, a randomized clinical investigation was performed to compare the Zip device with conventional suturing on patients with basal cell carcinoma, squamous cell carcinoma or dysplastic nevi [10]. The outcome indicated that the Zip device has equivalent cosmetic results as conventional suturing while being more time efficient regarding application and removal. Additionally, the study showed that the device can be removed by the patient, hence eliminating the need for a follow up visit for device removal.

During 2014 and 2015 a randomized clinical investigation was performed on pediatric patients who underwent cardiac operations [6]. The patients either received the Zip device or standard of care sutures as wound closure. The results showed that the greatest advantages with using the Zip device compared to sutures are the good cosmetic outcome and the reduced closure time. In addition, the Zip device was less painful during removal which can be particularly beneficial for a pediatric population.

Another randomized clinical investigation was performed in 2015 where the Zip device was compared with subcuticular sutures on patients undergoing cardiac implantable electronic defibrillator [8]. Results indicated significant time savings when using the Zip device instead of sutures, although scar outcome, pain ratings and patient satisfaction were similar in both groups.

A prospective evaluation was performed in 2015 on patients undergoing total knee arthroplasty and received the Zip device as skin closure system [11]. The results were compared to historical data of patients receiving sutures as wound closure. The outcome showed that the Zip device was easier to apply, had fewer wound complications, and that the device could be removed without a home care visit.

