8.4 Claim of the investigational device to be verified

Claim: Zip device significantly reduces treatment time of lacerations in pediatric population, and the significant reduction translates to a cost reduction for the A&E departments.

The primary endpoint will verify the time reduction of using the Zip device compared to standard of care sutures.

The second endpoints will verify:

- Physician and subject satisfaction of scar outcome and wound healing.
- Pain assessment during application and removal of device.

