9.3 Secondary endpoints (performance)

- Difference in Wound Evaluation Score at 10 days and 30 days post-treatment compare to baseline when comparing scar satisfaction and appearance of the subjects receiving Zip 4 Surgical Skin Closure Device versus Standard of Care closure suturing. The score will be based on digital photographs taken on day 0, day 10 and day 30 and made by an independent panel of blinded two specialists in plastic surgery.
- Rate of wound healing satisfaction in subject at 30 days post-treatment when comparing Zip
 4 Surgical Skin Closure Device versus Standard of Care closure suturing. The endpoint will
 utilize a questionnaire for the subject when possible or his caretakers to fill out.
- The level of pain in connection to device application and removal measured by a visual analog scale (VAS) 0-100 mm.

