subject's demographics. After confirmation of the inclusion and exclusion criteria the subject will be randomly assigned to either test or SoC group. Subject randomization procedure will take place in a block randomized fashion where equal numbers of subjects will receive the Zip 4 device and the SoC suture wound closure (1:1 ratio). The randomization will be performed by opening a sealed envelope containing a randomization card, for further details see *section 10.6.4*. The corresponding device written in the opened randomization envelope will be used as laceration repair.

Prior device application the wound will be cleansed, and for SoC subject local anesthesia and/or sedation will be used according to clinical routine. For Zip subjects, local anesthesia and/or sedation only will be used if deemed necessary by the Investigator. Photographs will be taken of the laceration by the study personnel, and thereafter the devices, Zip 4 device or SoC sutures, will be applied as according to the IFUs. After the devices have been applied appropriate, they will be covered with standard of care dressings to provide protection. Thereafter the subject will fill out the Visual Analog Scale (VAS) with assistance from the legal representative(s), if needed.

Prior discharge:

- Post-treatment information of the Zip 4 device or SoC sutures. The subjects and their legal representative(s) in the Zip 4 group will be informed that the subjects may not use ointments containing petroleum as well as reframe from soaking the device during baths or in swimming pools. Furthermore, the subject should not rub or continuously lay on the device since this may weaken the adhesives or damage the device.
- Removal of the Zip 4 device or SoC sutures will be conducted by the a study personnel either at Kaplan Medical Center ER or at the subjects home depending on the subjects preferences.
- The subject and their legal representative(s) will receive verbally and written information regrding the photgraphs that will be taken at day 10 and day 30.
- The subject and their legal representative(s) will receive questionnaires to be filled out at day 10 (VAS) and day 30 (Wound healing satisfaction questionnaire).
- The subject and their legal representative will be given contact information to the site in case of an adverse event or general questions concerning the investigation.

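### The protocol contradicts itself on who removes the Zip at day 10, and the VAS instruction as worded may rate current pain instead of pain during application and removal

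*Protocol*

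**What the plan says.** Two sets of statements matter: who takes the closure off at day 10, and what the child is asked to rate.

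On removal, 9.1 General (in a paragraph printed twice), note 5 to Table 3 in 9.8.1, and the discharge list in 9.8.1.1 all give removal of both closures to study staff. The last two allow it in the department or at home. Section 5.7 fits with these, since it describes the staff involved in removal as emergency physicians. Item 1 of 9.8.1.2 says otherwise: Zip families remove the device themselves at day 10 and may call for help. The closing checklist in 9.8.1.1 includes handing out Zip removal instructions. Item 2 of 9.8.1.2 has sutures removed in the department or at home and does not describe families removing them.

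On pain, 8.4 lists among the things the secondary endpoints will verify: "Pain assessment during application and removal of device". The rationale in 4.1 is that "the Zip device is less painful during removal which might be especially beneficial for a pediatric population", and 4.2 repeats it. The endpoint in 9.3 reads: "The level of pain in connection to device application and removal measured by a visual analog scale (VAS) 0-100 mm". The only rating instruction shown is in 9.8.3.4: "The subject will fill out the VAS line at the point that represents their pain intensity at the time", followed by "The VAS will be used after device has been applied at day 0, and after device removal at day 10". On day 0, 9.8.1.1 places the rating after closure and dressing: "Thereafter the subject will fill out the Visual Analog Scale (VAS) with assistance from the legal representative(s), if needed". Section 11.1 plans a between-arm t test on the VAS data.

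**The concern.** Both problems bear on the same planned comparison.

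The first is a direct contradiction in operative text. A site that follows 9.8.1.2 would have Zip devices peeled off by parents or children and sutures taken out by someone else. Any day-10 difference in VAS could then come from the closure or from the person removing it, and the data could not separate the two.

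The second is a possible mismatch between the claim and the measurement. The claim concerns pain while the closure is being applied and removed. The instruction, read naturally, records how much it hurts once that is over. If children rate it that way, the t test compares residual pain between arms and says little about the claim. What a child was asked cannot be changed at the analysis stage, so the wording has to be settled before data are collected.

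**Working it through.** No arithmetic applies. The only sample size (11.2, 12 per group) is for closure time, and no power is stated for VAS. The check is a comparison of the texts.

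**Who removes the Zip**

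- Study staff remove both closures: three separate places (9.1, whose paragraph appears twice and counts once; Table 3 note 5; the 9.8.1.1 discharge list). Section 5.7 is consistent with them.
- Zip families remove it themselves: one instruction (9.8.1.2 item 1), supported by one handout line (the closing checklist in 9.8.1.1).

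Section 9.8.1.1 therefore points both ways within itself. The follow-up 1 CRF page records whether the device stayed attached, the date and time of removal, whether this was on schedule, and use of adhesive remover. It has no field for who removed the closure.

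The conflict also touches care. Section 5.8 lets the physician at the day-10 follow-up leave the device on longer if the wound might gape. Removal by the family beforehand would bypass that decision.

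**What the VAS rates**

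1. Target in 8.4: pain during application and during removal.
2. Endpoint in 9.3: pain connected with those two events, a looser wording.
3. Instruction in 9.8.3.4: pain intensity at the moment of rating, on the natural reading.
4. Timing in 9.8.3.4: after application and after removal. By 9.8.1.1, the day-0 rating also follows the dressing.

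Items 3 and 4 together give current pain after the procedure. That can satisfy item 2 but not clearly item 1.

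**Whether another item fills the gap**

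The follow-up 1 interview asks about satisfaction with removal. Item 5 of the wound healing questionnaire asks how the treatment was experienced, and item 4 asks about pain in the scar at day 30. None of these measures procedural pain.

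**The case against.** The strongest case concerns the VAS. The last words of the 9.8.3.4 instruction could mean the time of application or removal, and the next sentence ties the scale to exactly those events. The endpoint as defined in 9.3 is compatible with a rating made straight afterwards. The line in 8.4 is one bullet in a list of claims and can itself be read as an assessment made on those two occasions. What a child rates is settled by the prompt on the VAS form, which the CRF mentions but which is not in the text at hand. All of this stands. It makes the VAS part an ambiguity and not a proven fault.

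On removal, the self-removal text looks like a remnant of incomplete editing, so a confounded design was probably never intended. Item 2 of 9.8.1.2 allows suture removal at home, so setting need not differ by arm. The CRF's separate visit and removal times, and its free-text comments, could leave an indirect trace of removal by the family. These points also stand, but the contradiction remains. With both instructions in force, either practice follows one section and breaches another.

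A reader might go further and infer that anaesthesia biases the day-0 score: under 9.8.1.1, "for SoC subject local anesthesia and/or sedation will be used according to clinical routine", while Zip subjects receive it only if the investigator judges it necessary. The documents do not support that inference. They give no duration of numbness, no rate of use by arm and no interval from closure to rating, so neither size nor direction can be stated. Sparing use of anaesthesia is also part of the Zip approach being compared, so an arm difference that arises from it is not automatically bias.

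**Conclusion.** The concern holds in two parts of unequal strength.

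The removal conflict is established by the text alone. Its consequence is conditional: remover is confounded with arm in the day-10 VAS comparison only if 9.8.1.2 is followed, and no dedicated CRF field would show that it was.

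The VAS wording is a likely mismatch with 8.4, resting on the natural reading of 9.8.3.4 and on the unseen form not supplying a procedural prompt. It would be too strong to say that the trial fails to measure procedural pain.

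Neither part can be quantified, because the protocol contains no pain data. The reach is one secondary endpoint; the primary endpoint of treatment time is untouched. Both should be corrected because the corrections are cheap and cannot be made after data collection.

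**What to change.** - In 9.8.1.2, have study staff remove both closures, in line with 9.1, Table 3 note 5 and the discharge list in 9.8.1.1.
- Delete the leftover self-removal, telephone and posted-form text wherever it stands: both copies of the 9.1 paragraph, 9.8.1.1, 9.8.1.2, 9.8.1.3, and the follow-up headings and Concomitant Medication Log instruction in the CRF. Editing only 9.8.1.1 and 9.8.1.2 would leave the protocol inconsistent.
- Add one field to the follow-up 1 CRF page for who removed the closure.
- In 9.8.3.4 and on the VAS form, ask for the pain felt during application (day 0) and during removal (day 10), rated promptly after each procedure.
- Report VAS beside the anaesthesia and sedation use that the CRF already records. No added data are needed.

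The cost is a sentence in 9.8.3.4, a prompt on the VAS form for each occasion, one CRF field and a set of deletions. The drawback is reliance on short recall, which is harder for the youngest children (entry is from age 4) and for sedated children, who would rate after waking.

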9.8.4 Safety Variables and Measurements

The safety measurement will be the onset, severity, duration and frequency of adverse events (anticipated and unanticipated), including determination of causality. The adverse event recordings between the two device groups will be compared. Only events, which are new after the consent has been signed or have increased in severity after the consent has been signed, will be recorded and used in the comparison. All adverse events will be recorded and reported and all data required both to assess the safety and to comply with the Competent Authority (CA) and IEC requirements will be collected.

9.8.5 Potential Confounding Factors

- Dressings will be used on the devices to provide protection, e.g. of accidental loss of device. If the device would be accidentally lost prior to complete healing process the outcome may be less favorable for the subject.

- Petroleum based ointments in conjunction with the Zip 4 device should not be used since the effects are unknown.

9.8.6 Prior and Concomitant Medication and Procedures

The site personnel will record the concomitant medication (using generic names) information in the appropriate section of the CRF.

Note that petroleum based ointments shall not be used in conjunction with this Zip device since the effects are unknown.

No other interactions are anticipated between treatment with the investigational device and concomitant medications and therefore there are no restrictions of concomitant medications.

10 DATA QUALITY ASSURANCE

10.1 Monitoring, Audits and Inspections

During the investigation, the monitor will have regular contacts with the investigation site. These contacts will include visits to confirm that the facilities remain adequate to specified standards and that the site personnel are carrying out the procedure as stated in the CIP. All data must be accurately recorded in the CRF. Source Data Verification (SDV), a comparison of data in the CRF with the subjects' medical records and other records of source data at the investigation site, will also be performed. The CRF and source documents and records must be made accessible during the visit.

The monitor and other Sponsor personnel will be available between visits if the PI or other site personnel needs information and/or advice. Authorized representatives of the Sponsor and/or appropriate regulatory agencies, including IEC, may visit the site to perform audits/inspections, including SDV.

A detailed description of the monitoring activities will be explained in investigation specific monitoring plan.

10.2 Subject Records and Source Data

Subject data recorded directly in the CRF, and not into the medical record, will be considered as source data. It is the responsibility of the PI to record essential information in the medical records, in accordance with national regulations and requirements. The origin of the source data in this clinical investigation will be further specified in a separate document ("Origin of Source Data").

In general, the following information will be recorded in the medical records:

- Clinical investigation code
- Subject identification number
- That informed consent for participating in the clinical investigation was obtained
- Diagnosis
- All visits during the investigation period
- All AEs/ADEs
- Treatments and medications

In the instance where the CRF is considered source data it should be noted on the "Origin of Source Data" document. The PI is responsible for ensuring the accuracy; completeness, legibility and timeliness of the data recorded in the CRFs. Completed sections of CRFs will be monitored and collected on regular basis.

